University of Kansas Medical Center
RESEARCH PROTOCOL INVOLVING HUMAN SUBJECTS
TEMPLATE WITH GUIDANCE

Version date: 2/19/2024

Principal Investigator: [name]

Study Title: Added sugar intake and brain structure and function

Co- Investigator(s): [name]

I. Purpose, Background and Rationale

A. Aim and Hypotheses

1. The first 1000 days post-conception have been characterized as a critical window for brain development, during which much of the brain's growth, structure, and function is set¹. Key nutrients from maternal and infant dietary intake fuels these maturational processes, thus providing the potential underlying foundation for later cognitive development. Brain growth and development is particularly sensitive to poor nutrition during this window²; previous work detailed the effects of deficiencies in the status of folic acid, choline, iron, zinc, iodine, and long chain polyunsaturated fatty acids³. While nutrient deficiencies have been studied, less is known about the impact and timing of excess nutrition in relation to cognitive development⁴.

2. Aim 1: Determine the relationship between added sugars (% calories) intake during pregnancy and infancy/toddlerhood (birth to 24 months) on brain structure and function.
Hypothesis: added sugars intake will be negatively related to brain structure (hippocampal volume) and function (resting state functional connectivity and P3 amplitude). We will explore how sex modifies this relationship.

Aim 2: Determine the relationship between fructose (% calories) consumption during pregnancy and infancy/toddlerhood (birth to 24 months) on brain structure and function. Since some studies reported relationships with fructose independently, we will explore relationships with fructose separately.

Hypothesis: fructose intake will be negatively related to brain structure (hippocampal volume) and function (resting state functional connectivity and P3 amplitude). We will explore how sex modifies this relationship.

B. Background and Significance

1. Study Significance: Brain development is a protracted process that begins in early gestation and continues into late adolescence. By the 8th week in gestation, the basic brain structures and the central nervous system are formed, and neuron production and migration are started⁵. From the 8th week until delivery, the cortical and subcortical structures form, including the major fiber pathways. In the third trimester, myelination

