Aim 1: Determine the relationship between added sugars (% calories) intake during pregnancy and infancy/toddlerhood (birth to 24 months) on brain structure and function.

Aim 2: Determine the relationship between fructose (% calories) consumption during pregnancy and infancy/toddlerhood (birth to 24 months) on brain structure and function.

Secondary Aims:

Secondary Aim 1: Determine the relationship between added sugars (% calories) intake during pregnancy and infancy/toddlerhood (birth to 24 months) on cognition.

B. Study Type and Design: This is a non-interventional, observational study.

Added sugar intake during pregnancy will be assessed using dietary data collected between 12-20 wks gestation using the National Cancer institute (NCI) DHQ-II food frequency questionnaire (FFQ) or three 24-hour dietary recalls.

Offspring dietary intake was collected at 2 weeks and at 6, 12, and 24 months by one multiple-pass 24-hour dietary recall administered to the child's caregiver and collected by trained research staff.

For the present study, we will collect three total dietary recalls: two weekday and one on the weekend.

Brain structure and function will be measured using MRI and EEG assessments. Cognition will be measured using dimensional change card sort task and Peabody picture vocabulary test.

C. Sample size, statistical methods, and power calculation

1. n/a – randomization will not be used
2. n/a – study will not be blinded
3. The present study is pilot. The planned sample size is 45 subjects.

D. Subject Criteria (See Vulnerable Populations appendix, if applicable): Participants who were previously enrolled in the ADORE GAINS study will be invited to participate in the present study when they are 5-6 years old. Participants will be both male and female and English or Spanish speaking.

1. Inclusion criteria: Participated in ADORE GAINS. Age 5-6.
2. Exclusion criteria: children who have received an autism diagnosis (per parent report)
3. Withdrawal/Termination criteria: n/a

4. Subjects may enter another research study while participating in this research study, as this study is observational only.

E. Specific methods and techniques used throughout the study

1. Laboratory tests: n/a
2. Study Procedures:

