D. Procedures to protect subject confidentiality: There is no appreciable risk of loss of confidentiality. Subjects will be made aware of persons who may see their protected health information in the informed consent document and may choose not to enroll in the study based on the information provided them in accord with 2003 HIPAA regulations. The patient's confidentiality will be maintained and will not be made publicly available to the extent permitted by the applicable laws and regulations.

E. Quality Assurance / Monitoring

1. All data entry will be verified by a second study team member using the original source document to ensure data are accurate, consistent, complete and reliable.
2. n/a – no plans to have ongoing third-party monitoring

V. Data Analysis and Reporting

A. Statistical and Data Analysis: The data analysis plan for each primary aim is described below. There are no planned interim analyses.

1. **Aim 1 analysis:** Determine the relationship between added sugars (grams and % calories) intake during pregnancy and infancy/toddlerhood (birth to 24 months) on brain structure and function. Brain structure will be quantified as brain volume in Freesurfer. Based on prior studies, we will examine the Pearson correlation between hippocampal brain volume and added sugars intake during pregnancy and infancy/toddlerhood. Exploratory analyses will examine correlations with added sugars intake and brain volume in inhibitory control brain regions (i.e., dorsal anterior cortex) and reward related regions (i.e., ventromedial prefrontal cortex). Brain function will be quantified as resting state functional connectivity within the default mode network which includes prefrontal and parietal regions as well as the attention and salience networks. Pearson correlations will examine the relationship between functional connectivity metrics and added sugars intake. Brain function during the EEG Food Go/NoGo task will be quantified as the amplitude of the P3 and N2 components and correlations will examine the relationship between P3/N2 amplitudes and added sugars. Analyses will be corrected for multiple comparisons using a Bonferroni correction.

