2. **Aim 2 analysis:** Determine the relationship between fructose (grams and % calories) consumption during pregnancy and infancy/toddlerhood (birth to 24 months) on brain structure and function. As in Aim 1 analyses, brain structure will be quantified as Freesurfer volumes, brain function will be quantified as resting state connectivity, and brain activation during the EEG Food Go/NoGo Task. Correlations will be used to examine the relationship between brain measures and fructose consumption.

B. Outcome: We hypothesize that added sugars and fructose intake will be negatively related to brain structure (hippocampal volume) and function (resting state functional connectivity and P3 amplitude). The strength of the correlations and level of significance will determine if there is a relationship between variables being tested.

C. Study results to participants: Study participants will be informed of the overall study results via a letter, which will be mailed after the study and analysis is complete. Participants will not be given their individual results from study procedures; however, this information may be made available upon request, with approval by the PI.

D. Publication Plan: The present study is a pilot. This project was submitted as a June 2022 R01 and received positive reviews. It will be resubmitted in November 2022 with the hope of receiving R01 funding to extend the study to the entire ADORE GAINS cohort. We hope by getting more participants to complete the cognitive tests and body composition measurements that we will have a large enough sample to publish results relating to those

measurements. Any publications would further support the R01 application.

VI. Literature Cited

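### The planned correlations of Freesurfer hippocampal volume with intake take no visible account of head size, so they cannot show whether an association is specific to the hippocampus.

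*Combined protocol and SAP*

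**What the plan says.** For Aim 1, Section V.A.1 defines the structural measure: "Brain structure will be quantified as brain volume in Freesurfer". It then gives the test: "we will examine the Pearson correlation between hippocampal brain volume and added sugars intake during pregnancy and infancy/toddlerhood". Exploratory correlations with the volumes of inhibitory-control and reward regions follow the same pattern. For Aim 2, Section V.A.2 repeats that "brain structure will be quantified as Freesurfer volumes" and names correlations as the method for fructose.

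The hypotheses in Sections I.A.2 and V.B name hippocampal volume as the structural outcome and predict a negative relation with intake. Section V.B gives the decision rule: "The strength of the correlations and level of significance will determine if there is a relationship between variables being tested". The only adjustment named is for multiplicity: "Analyses will be corrected for multiple comparisons using a Bonferroni correction". The number of tests is not stated.

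On the sample, Section II.C says "The present study is pilot. The planned sample size is 45 subjects". Section II.D limits age to 5-6 years and says "Participants will be both male and female". Sex is to be explored as a modifier (Section I.A.2), but Section V.A gives no analysis for it. No visible text mentions intracranial volume, total brain volume, a ratio, a residual, a partial correlation or any covariate.

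**The concern.** An absolute regional volume reflects both the region and the size of the head that contains it. The hypothesis names the hippocampus, and the decision rule looks only at the strength and significance of one correlation. Nothing in that rule tells a reader whether the hippocampus differs in its own right or only in proportion to the head.

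There are two possible consequences. First, if intake is unrelated to head size, head-size variation is noise for a hippocampus-specific question, and a sample of 45 has little precision to spare. Second, if intake is related to head size, the unadjusted correlation mixes two associations and can overstate or understate the hippocampal one. The same applies to the exploratory regions and to Aim 2. Section V.D says the pilot is meant to support funding to extend the work to the whole cohort, so an ambiguous result would carry forward into that design.

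**Working it through.** The plan states no alpha, sidedness, effect size or power, so there is no figure of its own to reproduce.

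**Input from the documents:** n = 45 (Section II.C).

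**Assumptions, not in the documents:** two-sided alpha 0.05; ρ, the correlation of hippocampal volume with head size, 0.4 to 0.6; g, the correlation of intake with head size, zero or as stated; a true head-size-adjusted (partial) correlation p of size 0.40 where one is needed.

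**Formulas**
- Unadjusted correlation: r = p × √[(1 − ρ²)(1 − g²)] + ρg.
- Power by Fisher z: Φ(|atanh r| × √(n − 3) − 1.96). For a partial correlation on one covariate, n − 4 replaces n − 3.
- Critical |r| at n = 45: tanh(1.96/√42) = 0.294.

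**1. Intake unrelated to head size (g = 0).** Adjusted: atanh 0.40 = 0.4236; 0.4236 × √41 = 2.713; Φ(2.713 − 1.96) = 77%. Unadjusted:

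| ρ | r = 0.40 × √(1 − ρ²) | atanh r × √42 | Power |
|---|---|---|---|
| 0.4 | 0.367 | 2.492 | 70% |
| 0.5 | 0.346 | 2.342 | 65% |
| 0.6 | 0.320 | 2.149 | 57% |

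Over a wider range, ρ = 0.3 gives 74% and ρ = 0.7 gives 48%. A simulation (40,000 replicates, t-tests) gave 75%, 66% and 48% unadjusted at ρ = 0.3, 0.5 and 0.7, and 78-79% adjusted.

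**2. No hippocampus-specific association (p = 0), intake related to head size.** Then r = ρg. At ρ = 0.4 and |g| = 0.1, |r| = 0.04 and the unadjusted test rejects in about 6% of studies. At ρ = 0.5 and |g| = 0.3, |r| = 0.15 and it rejects in 17%. At ρ = 0.6 and |g| = 0.3, |r| = 0.18 and it rejects in 22%. In simulation at |g| = 0.3, the adjusted test rejected in 5%.

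**3. Masking.** With p = −0.40, ρ = 0.5 and g = +0.2: r = −0.40 × √(0.75 × 0.96) + 0.10 = −0.24, and unadjusted power is 35%.

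**4. The reverse case.** Fix the total correlation at −0.40 with ρ = 0.5. The partial correlation is (−0.40 − 0.5g)/√[0.75 × (1 − g²)]. For g = −0.2 this is −0.30/√0.72 = −0.35; for g = −0.3 it is −0.25/√0.6825 = −0.30. Unadjusted power is 78%. Adjusted power is 66% and 52%.

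Case 1 favours adjustment for power and case 4 favours the unadjusted volume. What separates them is whether intake is related to head size, and the documents do not say.

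**The case against.** The strongest objection is about the question being asked. The documents never say that the hippocampal association must be independent of head size. The aims concern brain structure in general, and a hippocampus that is smaller because the whole brain is smaller is still associated with intake. Exposure runs from pregnancy to 24 months and the scan is at 5-6 years, so head size is measured after exposure and may lie on the causal path. The protocol's own literature review (Section I.B.3) cites lower newborn gray matter with higher prenatal added sugars. Adjustment could then remove part of the effect sought, as case 4 shows. This stands. It is why the unadjusted correlation has to be kept and reported beside the adjusted one.

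Two stronger readings are tempting. A reader might infer that head size will dilute or imitate the hippocampal result, and that the rejections in case 2 are simply false positives. The documents do not support this. Both key correlations are assumed, and the harm is small at their low end (0.40 becomes 0.37; 5% becomes 6%). The 22% is the extreme corner of the range and takes no account of the promised Bonferroni correction. Over six tests, an assumed count, that corner is about 7% per test against a nominal 0.8%. An imitation would support the stated hypothesis only if intake were negatively related to head size. The rejections are also false only for a hippocampus-specific claim, not for a total association.

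A reader might also infer that the study has no scaling step at all. References 60-64, which include MRI and EEG methods, are listed but not cited in the text available for review, so imaging detail may exist that is not visible here. The gap is shown only for the visible text, but that includes Section V.A, which defines both measure and test. If scaling is described elsewhere, Section V.A should say so.

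That this is a pilot with no power claim limits the consequence but does not remove the ambiguity.

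**Conclusion.** The point holds in a conditional form. As written, Sections V.A.1 and V.A.2 cannot distinguish a hippocampus-specific association from a proportional difference in head size. That follows from the stated measure and test and needs no assumed figure.

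The statistical cost is conditional. If intake is unrelated to head size, the loss is 7 to about 20 percentage points of power (77% to 70-57%), given ρ of 0.4 to 0.6, a true adjusted correlation of 0.40, n = 45 and a two-sided 5% test. If intake is related to head size, the unadjusted result can imitate or mask a hippocampus-specific association. Adjustment can then lower power when the effect works through whole-brain growth. Size and direction depend on correlations the documents do not give. The change is worth making because it is nearly free and settles the interpretation before the data are seen.

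**What to change.** In Sections V.A.1 and V.A.2, prespecify the correlation of hippocampal volume with intake, adjusted for estimated intracranial volume from the same Freesurfer run (partial correlation or regression), as the test of a hippocampus-specific association. Do the same for the exploratory regional volumes. Report the unadjusted volume correlation alongside as the total association. State in advance that a finding present only in the unadjusted result will not be read as hippocampus-specific.

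The cost is a sentence or two in Section V.A and one degree of freedom per test, with no new data or visits. The adjusted result removes any effect that acts through overall brain growth, which is the reason for reporting both.

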In 7-11-year-old children⁴⁸, increased intake of fructose and glucose was associated with increased right hippocampal CA2/3 subfield volume, and increased fructose intake was associated with mean diffusivity in the right cingulate-prefrontal cortex connections. This suggests an impact on hippocampal structure related to an increase in hippocampal inflammation. In the Project Viva cohort⁵⁵, greater maternal prenatal intake of SSB was related to poorer offspring global intelligence. Greater maternal prenatal added sugars consumption was also related to lower newborn gray matter at 3 weeks old, including areas for later cognitive functioning³⁴, suggesting an impact on formation of dendrites and synapses. This cohort was tested again at 24 months using the Bayley-III Scales of Infant Development⁵⁶. Greater maternal SSB intake was related to lower scores on the Bayley-III. These data provide evidence for a relationship between maternal added sugars intake and the brain structures that are the foundation for future cognitive development.

C. Rationale

1. As described above, there is a growing body of evidence to suggest that excess added sugar intake negatively affects cognition.
2. The innovation for this proposal involves a shift with respect to the theoretical approach around the relationship between cognition and nutrition. *While the impact of key nutrient deficiencies on cognition is well documented, the relationship between excess intake (i.e., added sugars) and cognitive development has not been previously studied.* Further, data are lacking on exposure timing relative to the impact on cognition and brain

development. This proposal will investigate three time periods that are well established windows of brain development that are sensitive to nutrient exposures: the prenatal, infancy, and toddlerhood time periods.

3. n/a – this study is not designed to improve the diagnosis or treatment of a disease

II. Research Plan and Design

A. Study Objectives: This purpose of this study is to fill a gap in the literature by providing an understanding of the relationship between added sugars and fructose intake during sensitive windows to brain structure and function. This project is unique because we can determine the effect of added sugars during three different times: pregnancy, infancy, and toddlerhood.

Primary Aims:

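### The one Bonferroni sentence defines no family, divisor, alpha or sidedness and leaves coverage of primary Aim 2 unclear, while grams, N2 and possibly separate networks enlarge the test set

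*Combined protocol and SAP*

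**What the plan says.** Section II.A lists two primary aims, one for added sugars and one for fructose. Both express exposure as % of calories; for fructose: "Determine the relationship between fructose (% calories) consumption during pregnancy and infancy/toddlerhood (birth to 24 months) on brain structure and function". The hypotheses in I.A name three outcomes for each aim: hippocampal volume, resting-state connectivity and P3 amplitude. They also announce, for each aim: "We will explore how sex modifies this relationship".

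The analysis text in V.A is wider.

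- **Exposure scale.** The Aim 1 item opens: "Determine the relationship between added sugars (grams and % calories) intake during pregnancy and infancy/toddlerhood (birth to 24 months". The Aim 2 item likewise uses both grams and % calories.
- **EEG.** The Food Go/NoGo measure is "quantified as the amplitude of the P3 and N2 components", whereas the hypothesis names only P3.
- **Connectivity.** The default mode, attention and salience networks are mentioned in one sentence. It can be read as three measures or as one composite.
- **Exposure windows.** V.A names pregnancy and a combined infancy/toddlerhood period. II.A says: "This project is unique because we can determine the effect of added sugars during three different times: pregnancy, infancy, and toddlerhood".
- **Multiplicity.** The last sentence of the Aim 1 item is "Analyses will be corrected for multiple comparisons using a Bonferroni correction". The Aim 2 item has no such sentence. Its cross-reference concerns measurement: "As in Aim 1 analyses, brain structure will be quantified as Freesurfer volumes, brain function will be quantified as resting state connectivity". It ends: "Correlations will be used to examine the relationship between brain measures and fructose consumption".

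V.B then makes the strength of the correlations and their significance level the basis for deciding whether a relationship exists, with no threshold for either. II.C gives 45 subjects and describes a pilot.

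**The concern.** Bonferroni cannot be carried out without a number of tests and an alpha, and the plan gives neither. Several counts are defensible from its text, so the same observed correlation can be declared significant or not according to a count fixed after the results are known.

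The broad reading also has a price. Grams and % calories are two scalings of the same intake, and N2 is not in the hypotheses. If they enter the divisor, the hypothesised tests pay for them in a small sample.

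This is an observational pilot. What is at stake is the credibility of its stated conclusions and of the follow-on grant application described in V.D, not patient safety.

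**Working it through.** **No figure to reproduce.** The plan prints no alpha, divisor, effect size or power. The sample size of 45 stands alone.

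**Inputs.** From the plan: n = 45 (II.C), and the outcomes, windows and scales listed above. Assumed: familywise alpha 0.05, two-sided, complete data, and an illustrative true correlation of 0.4.

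**Step 1: count the Aim 1 tests** as outcomes × windows × scales.

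- Hypothesised set, % calories: 3 × 2 × 1 = 6. With three windows, 3 × 3 × 1 = 9.
- Add grams and N2, connectivity as one composite: 4 × 2 × 2 = 16.
- Add grams and N2, three separate networks: 6 × 2 × 2 = 24.

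The two example regions labelled exploratory are left out. If the unqualified correction sentence took them in as well, the last count would be 8 × 2 × 2 = 32.

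**Step 2: critical correlation.** With t the two-sided critical value at 0.05/m on 43 df, critical |r| = t/√(43 + t²).

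**Step 3: power for a true r = 0.4**, by Fisher z: Φ(atanh(0.4) × √42 − z), where z is the normal critical value at 0.05/m. Here atanh(0.4) × √42 = 0.4236 × 6.481 = 2.746. For m = 6, z = 2.638 and power is Φ(0.108) = 54%. For m = 16, z = 2.955 and power is Φ(−0.209) = 42%. For m = 24, z = 3.078 and power is Φ(−0.332) = 37%.

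**Step 4: an observed |r| = 0.42.** t = 0.42 × √(43/(1 − 0.1764)) = 3.035, so unadjusted p = 0.00407. Multiply by m.

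| Tests m | 0.05/m | Critical \|r\| | Power, true r = 0.4 | Adjusted p, \|r\| = 0.42 |
|---|---|---|---|---|
| 6 | 0.00833 | 0.389 | 54% | 0.024 |
| 9 | 0.00556 | 0.407 | 49% | 0.037 |
| 12 | 0.00417 | 0.419 | 45% | 0.049 |
| 16 | 0.00313 | 0.431 | 42% | 0.065 |
| 24 | 0.00208 | 0.447 | 37% | 0.098 |

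The m = 12 row is the six hypothesised tests taken over both aims as one family. A single uncorrected test would have critical |r| 0.294 and power 78%.

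**Step 5: sensitivity to the assumptions.** For m = 6, 16 and 24 at n = 45, power is 26%, 17% and 14% if the true r is 0.3, and 82%, 73% and 69% if it is 0.5. The plan does not say how many children will have usable MRI and EEG data. With true r = 0.4 and an assumed n = 36 (√33 in place of √42), power is 42%, 30% and 26%; with n = 25 (√22), it is 26%, 17% and 14%.

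**Step 6: precision of a null result.** At n = 45 an observed r = 0 has a 95% interval of ±tanh(1.96/√42), about −0.29 to +0.29.

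**The case against.** **It is a pilot, and a one-line clarification would do.** The pilot status limits the consequence. But the plan itself chose significance testing with a correction and made significance a decision criterion in V.B, so the threshold must be defined.

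**The word Analyses already covers Aim 2.** This is the more natural reading. It still leaves the divisor open, and open whether it applies per aim or across both. A reader might go further and infer that Aim 2 is tested uncorrected; with six independent tests and all nulls true, the chance of at least one false positive would then be 1 − 0.95⁶ = 26%. The documents do not establish that reading. They are silent on coverage, so the figure is conditional and the conclusion here does not use it.

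**The networks may be one composite measure.** This stands. V.A.1 may only be specifying the hypothesised connectivity outcome, so it cannot be taken as settled that the networks multiply the tests. The count of 16 covers the composite case, and the conclusion survives it.

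**A single family over both aims is a preference.** This also stands. I.A says fructose relationships will be explored separately, which supports one family per aim even though II.A lists both aims as primary.

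**Six tests is not a real count while the measures are undefined.** Correct. II.B gives child recalls at 2 weeks and at 6, 12 and 24 months, and V.A has no rule for combining them. Which hippocampal measure and which P3 measure will be used is also not stated. The fix has to settle these.

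**Conclusion.** The concern holds. The plan's only multiplicity rule cannot be executed as written, and its reach over the second primary aim is not stated. For Aim 1 with two windows, the divisor is 6 for the hypothesised set and 16 or 24 for everything non-exploratory. That costs 12 or 17 percentage points of power for a true r of 0.4 (54% to 42% or 37%), and it reverses the conclusion for an observed |r| of 0.42. These sizes assume two-sided 0.05 and complete data on 45 children; fewer usable scans or EEG recordings would lower all the power figures.

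The text does not support saying that Aim 2 is definitely uncorrected, that the three networks are definitely separate tests, or that the two aims must share one family. The point should be corrected before analysis, and it bears on interpretation only.

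**What to change.** In V.A, before any analysis, state: *Two-sided familywise alpha 0.05 by the Holm procedure, applied to both primary aims. Family for each aim: intake as % calories, in pregnancy and from birth to 24 months, against hippocampal volume, one named connectivity measure and P3, giving 6 tests.*

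- **Across the aims.** One family per aim is acceptable if the plan states that the overall error may reach about 10% (0.05 + 0.05). A single 12-test family is the stricter alternative, with first-step power of 45% instead of 54% for r = 0.4.
- **Make the count real.** Fix in advance one summary of the 2-week and 6-, 12- and 24-month recalls, one hippocampal measure, one connectivity measure and one P3 measure. If the three periods in II.A are meant to be confirmatory, use 3 × 3 = 9 tests per aim (first-step power 49%).
- **Everything else.** Report grams, N2, additional networks and regions, and sex modification as exploratory estimates with 95% confidence intervals and no significance claim.
- **Section V.B.** Report every correlation with its 95% confidence interval, and do not read a non-significant result as absence of a relationship.

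The cost is wording in V.A and V.B, with no new data. Grams, N2 and any additional networks lose confirmatory status. Holm rejects everything Bonferroni rejects on the same family, so that change costs nothing.

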2. The impact of excess nutrient intake on brain development and function has garnered far less consideration compared to nutrient deficiencies. Data suggest that added sugars intake during pregnancy, infancy, and toddlerhood may interfere with the early formation of the brain structures that contribute to learning and memory³⁴. Fructose is of particular interest here, as it is one of six monosaccharides represented in added sugars³⁵, and is found in the diet as a sweetener commonly added to foods during processing in the form of high fructose corn syrup (HFCS) and sucrose, a disaccharide made of a glucose bound to a fructose³⁶. HFCS is a low-cost sweetener commonly used in sugar sweetened beverages (SSB). The effect of fructose may be due to fructose metabolism not being tightly regulated like glucose metabolism³⁶ leading to oxidative stress and an inflammatory response³⁷.
3. Literature Review: The literature suggests that added sugars intake in early life exceeds recommendations. Added sugars are defined as sugars and syrups added as an ingredient to foods during processing, preparation, or at the table, while total sugars include added sugars plus sugar naturally occurring in foods (e.g., fruit and milk)³⁵. One added sugar in particular, fructose (e.g., high fructose corn syrup), has been investigated as a driver of the negative relationships reported between added sugars and health outcomes³⁸. Pregnant women are recommended to consume <10% of calories/day from added sugars, whereas infants and toddlers (<24 months) are recommended to consume no added sugars³⁹. Even so, pregnant women are reported to consume 15.8% of calories/day from added sugars⁴⁰, and 6- to 24-month-olds to consume 1.4-7.2% of calories/day from added sugars^{41,42}. Data in pregnant women and infants and toddlers

found 70% of pregnant women³⁹ and 97.3% of infants and toddlers consumed added sugars in each day⁴³. While this is concerning given the relationships between added sugars intake and chronic disease development⁴⁴⁻⁴⁶, evidence is growing that early added sugars intake is also related to diminished cognitive function⁴⁷.

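### Aim 2 tests fructose only by marginal correlations, which cannot show whether fructose matters beyond the added sugars tested in Aim 1

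*Combined protocol and SAP*

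**What the plan says.** Sections I.A.2 and II.A list two primary aims with the same brain outcomes: Aim 1 for added sugars, Aim 2 for fructose.

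- **Overlap of the exposures.** Section I.B.2 says of fructose that "it is one of six monosaccharides represented in added sugars". Section I.B.3 adds that fructose "has been investigated as a driver of the negative relationships reported between added sugars and health outcomes".
- **Reason for Aim 2.** Section I.A.2: "Since some studies reported relationships with fructose independently, we will explore relationships with fructose separately".
- **Analysis.** For Aim 1, section V.A.1 states that "we will examine the Pearson correlation between hippocampal brain volume and added sugars intake during pregnancy and infancy/toddlerhood", with further correlations for connectivity and EEG measures. For Aim 2, section V.A.2 states: "Correlations will be used to examine the relationship between brain measures and fructose consumption".
- **Decision rule.** Section V.B: "The strength of the correlations and level of significance will determine if there is a relationship between variables being tested". No numerical alpha is given.
- **Multiplicity.** The Aim 1 text ends: "Analyses will be corrected for multiple comparisons using a Bonferroni correction". The number of tests is not stated, and the sentence is not repeated for Aim 2.
- **Size.** Section II.C.3: "The present study is pilot. The planned sample size is 45 subjects".

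The plan contains no partial correlation, joint model or comparison of the two sets of correlations. It does not plan to report how strongly the two exposures correlate.

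**The concern.** Within an exposure window, fructose and added-sugar intakes are partly the same quantity, and section II.B names no separate instrument for fructose. In pregnancy both are the mother's intake, from a questionnaire or recalls. From birth to 24 months both are the child's, from recalls. A marginal correlation with a part can inherit the association of the whole, and the reverse is also true.

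Two marginal correlations therefore cannot separate two situations: fructose carries the relationship, or fructose merely travels with added sugars. Yet the stated reason for a separate aim is that fructose has shown relationships of its own. If both correlations are significant, Aim 2 could be reported as a second finding about fructose, or as corroboration of Aim 1, when the data cannot distinguish it from Aim 1. Section V.D says the pilot is meant to lead to a funded extension to the whole parent cohort, so such a reading could shape the larger study.

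**Working it through.** The plan gives no power figure, effect size or exposure correlation, so there is no figure of its own to reproduce. What follows shows how large the problem could be.

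**Input from the documents:** n = 45 (II.C.3).

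**Assumptions:** two-sided alpha 0.05, with 0.05/6 as an illustrative Bonferroni threshold; true added-sugars correlation r with the brain measure of 0 to -0.4; fructose/added-sugar correlation ρ of 0.6 to 0.9, with 0.3 for weak overlap; normal data.

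**Step 1. Marginal fructose correlation when fructose adds nothing.** If fructose is unrelated to the outcome given added sugars, its marginal correlation is r × ρ. At r = -0.4 this is -0.24, -0.32 and -0.36 for ρ = 0.6, 0.8 and 0.9.

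**Step 2. Chance of significance.** By Fisher's z, power ≈ Φ(atanh|rρ| × √(n-3) - 1.960), with √42 = 6.481:

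- ρ = 0.6: 0.2448 × 6.481 = 1.586; Φ(-0.374) ≈ 35%
- ρ = 0.8: 0.3316 × 6.481 = 2.149; Φ(0.189) ≈ 57%
- ρ = 0.9: 0.3769 × 6.481 = 2.442; Φ(0.482) ≈ 69%

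Simulation (40,000 samples per setting) gives 36%, 58% and 70%. Simulated rates across the assumed range:

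| True added-sugars r | ρ = 0.6 | ρ = 0.8 | ρ = 0.9 |
|---|---|---|---|
| 0 | 5% | 5% | 5% |
| -0.2 | 12% | 18% | 22% |
| -0.3 | 22% | 36% | 44% |
| -0.4 | 36% | 58% | 70% |
| -0.4, alpha 0.05/6 | 15% | 31% | 43% |

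At ρ = 0.3 and r = -0.4 the rate at 0.05 is about 12%.

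**Step 3. Given a significant Aim 1 result at 0.05.** Fructose is also significant in about 35%, 61% and 77% of samples at r = -0.3, and in 43%, 71% and 85% at r = -0.4 (ρ = 0.6, 0.8, 0.9), although it adds nothing.

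**Step 4. The partial correlation.** With F fructose, S added sugars and Y the brain measure:

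r(FY|S) = (r(FY) - r(SY) ρ) / √[(1 - r(SY)²)(1 - ρ²)]

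When fructose adds nothing this is zero in truth, and its test rejects in about 5% of samples in every setting.

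**Step 5. What the partial test can detect.** If fructose is the sole driver at r = -0.4, the true partial correlation is r√(1-ρ²)/√(1-r²ρ²). For ρ = 0.6 its size is 0.4 × 0.8 / √(1 - 0.0576) = 0.330; for ρ = 0.8 and 0.9 it is 0.253 and 0.187. Simulated power at n = 45 is 60%, 39% and 23%, so the test misses in 40%, 61% and 77% of studies.

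**The case against.** The strongest reply is that the Aim 2 hypothesis says only that fructose is negatively associated with the brain measures, and a marginal correlation is a valid test of that. The documents nowhere promise to show an effect beyond added sugars. The remark about fructose as a driver is literature background, and looking at fructose separately can simply mean looking at it on its own. This stands as a defence of the test. It leaves open how the result is to be read, because nothing in V.B stops a significant correlation from being taken as specific to fructose.

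A reader might infer that spurious fructose findings will be frequent. The documents do not support that. Frequency needs both a sizeable true added-sugars relationship and a strong exposure correlation, and neither is given. The Aim 2 exposure is also not limited to added fructose. Section I.B.3 separates added sugars from sugars occurring naturally in foods such as fruit, and natural fructose may weaken the overlap. The stated Bonferroni correction, if it covers Aim 2, lowers the rate further.

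This is also a small pilot, and the publication hope in V.D names cognitive and body-composition results. That limits the urgency, but the remedy uses data already collected.

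**Conclusion.** The point holds as a gap between the reason given for Aim 2 and what its analysis can show. The planned correlations answer whether fructose is related to the brain measures. They cannot answer whether it matters beyond added sugars.

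How often this would mislead depends on assumptions. At n = 45, two-sided 0.05 and an exposure correlation of 0.6 to 0.9, a fructose result with nothing of its own behind it is significant in 12-22%, 22-44% or 36-70% of studies for a true added-sugars r of -0.2, -0.3 or -0.4. It is 15-43% at r = -0.4 under an illustrative 0.05/6. The exposure is greatest once Aim 1 is significant: 35-77% at r = -0.3 and 43-85% at r = -0.4. With no added-sugars effect it is the nominal 5%.

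Two stronger readings go too far: that the Aim 2 test is invalid, and that a partial interval including zero proves fructose to be the same signal as added sugars. The second treats non-significance as equivalence. At r = -0.4 with fructose the sole driver, it would mislabel 40-77% of studies.

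**What to change.** **In V.A.2:** report beside each fructose correlation its partial correlation given added sugars (both as % calories, same exposure window) with a 95% CI. Report the fructose/added-sugar correlation for each window.

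**In V.B:** state that a marginal fructose correlation alone supports no fructose-specific claim. Where the partial interval includes zero, report the result as *not distinguishable from the added-sugars association at this sample size*, and not as the same signal.

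**Cost:** a few lines of text, with no new data, visits or participants. The adjusted estimate will be imprecise at n = 45: power is about 23-60% if fructose is the true driver at r = -0.4. It should be presented as an estimate with its interval, not as a pass/fail test, and fructose-specific claims will be harder to make.
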